6.5.1 Rescue Medications and Supportive Care

Participants should receive appropriate supportive care measures as deemed necessary by the treating investigator. Suggested supportive care measures for the management of AEs with potential immunologic etiology are outlined along with the dose modification guidelines in Section 6.6.1, [Table 4](#). Where appropriate, these guidelines include the use of oral or IV treatment with corticosteroids, as well as additional anti-inflammatory agents if symptoms do not improve with administration of corticosteroids. Note that several courses of steroid tapering may be necessary as symptoms may worsen when the steroid dose is decreased. For each disorder, attempts should be made to rule out other causes such as metastatic disease or bacterial or viral infection, which might require additional supportive care. The treatment guidelines are intended to be applied when the investigator determines the events to be related to pembrolizumab.

Note: If after the evaluation of the event, it is determined not to be related to pembrolizumab, the investigator does not need to follow the treatment guidance. Refer to [Table 4](#) in Section 6.6.1 for guidelines regarding dose modification and supportive care.

It may be necessary to perform conditional procedures such as bronchoscopy, endoscopy, or skin photography as part of evaluation of the event.

Refer to Appendix 7 for country-specific requirements.

6.6 Dose Modification (Escalation/Titration/Other)

6.6.1 Immune-Related Events and Dose Modification (Withhold, Treat, Discontinue)

Dose Modification and Toxicity Management for Non-hepatic Immune-related AEs Associated with Pembrolizumab

AEs associated with pembrolizumab exposure may represent an immune-related response. These irAEs may occur shortly after the first dose or several months after the last dose of pembrolizumab treatment and may affect more than one body system simultaneously. Therefore, early recognition and initiation of treatment is critical to reduce complications. Based on existing clinical study data, most irAEs were reversible and could be managed with interruptions of pembrolizumab, administration of corticosteroids and/or other supportive care. For suspected irAEs, ensure adequate evaluation to confirm etiology or exclude other causes. Additional procedures or tests such as bronchoscopy, endoscopy, skin biopsy may be included as part of the evaluation. Based on the severity of irAEs, withhold or permanently discontinue pembrolizumab and administer corticosteroids.

Dose Modification and Toxicity Management Guidelines for Non-hepatic irAEs associated with pembrolizumab monotherapy, coformulations, or IO combinations are provided in [Table 4](#).

Table 4 Dose Modification and Toxicity Management Guidelines for Non-hepatic Immune-related Adverse Events Associated with Pembrolizumab Monotherapy, Coformulations or IO Combinations

General instructions: 1. Severe and life-threatening irAEs should be treated with IV corticosteroids followed by oral steroids. Other immunosuppressive treatment should begin if the irAEs are not controlled by corticosteroids. 2. Pembrolizumab monotherapy, coformulations or IO combinations must be permanently discontinued if the irAE does not resolve or the corticosteroid dose is not ≤ 10 mg/day within 12 weeks of the last treatment. 3. The corticosteroid taper should begin when the irAE is \leq Grade 1 and continue at least 4 weeks. 4. If pembrolizumab monotherapy, coformulations or IO combinations have been withheld, treatment may resume after the irAE decreased to \leq Grade 1 after corticosteroid taper.				
irAEs	Toxicity Grade (CTCAEv4.0)	Action With Pembrolizumab Monotherapy, Coformulations or IO Combinations	Corticosteroid and/or Other Therapies	Monitoring and Follow-up
Pneumonitis	Grade 2	Withhold	
 Administer corticosteroids (initial dose of 1-2 mg/kg prednisone or equivalent) followed by taper 	
 Monitor participants for signs and symptoms of pneumonitis Evaluate participants with suspected pneumonitis with radiographic imaging and initiate corticosteroid treatment Add prophylactic antibiotics for opportunistic infections
	Recurrent Grade 2 or Grade 3 or 4	Permanently discontinue		
Diarrhea / Colitis	Grade 2 or 3	Withhold	
 Administer corticosteroids (initial dose of 1-2 mg/kg prednisone or equivalent) followed by taper 	
 Monitor participants for signs and symptoms of enterocolitis (ie, diarrhea, abdominal pain, blood or mucus in stool with or without fever) and of bowel perforation (ie, peritoneal signs and ileus) Participants with \geq Grade 2 diarrhea suspecting colitis should consider GI consultation and performing endoscopy to rule out colitis Participants with diarrhea/colitis should be advised to drink liberal quantities of clear fluids. If sufficient oral fluid intake is not feasible, fluid and electrolytes should be substituted via IV infusion.
	Recurrent Grade 3 or Grade 4	Permanently discontinue		

irAEs	Toxicity Grade (CTCAEv4.0)	Action With Pembrolizumab Monotherapy, Coformulations or IO Combinations	Corticosteroid and/or Other Therapies	Monitoring and Follow-up
T1DM or Hyperglycemia	New onset T1DM or Grade 3 or 4 hyperglycemia associated with evidence of β -cell failure	Withhold ^a	
 Initiate insulin replacement therapy for participants with T1DM Administer anti-hyperglycemic in participants with hyperglycemia 	
 Monitor participants for hyperglycemia or other signs and symptoms of diabetes
Hypophysitis	Grade 2	Withhold	
 Administer corticosteroids and initiate hormonal replacements as clinically indicated 	
 Monitor for signs and symptoms of hypophysitis (including hypopituitarism and adrenal insufficiency)
	Grade 3 or 4	Withhold or permanently discontinue ^a		
Hyperthyroidism	Grade 2	Continue	
 Treat with non-selective beta-blockers (eg, propranolol) or thionamides as appropriate 	
 Monitor for signs and symptoms of thyroid disorders
	Grade 3 or 4	Withhold or Permanently discontinue ^a		
Hypothyroidism	Grade 2-4	Continue	
 Initiate thyroid replacement hormones (eg, levothyroxine or liothyronine) per standard of care 	
 Monitor for signs and symptoms of thyroid disorders
Nephritis and renal dysfunction	Grade 2	Withhold	
 Administer corticosteroids (prednisone 1-2 mg/kg or equivalent) followed by taper 	
 Monitor changes of renal function
	Grade 3 or 4	Permanently discontinue		

irAEs	Toxicity Grade (CTCAEv4.0)	Action With Pembrolizumab Monotherapy, Coformulations or IO Combinations	Corticosteroid and/or Other Therapies	Monitoring and Follow-up
Myocarditis	Grade 1	Withhold	
Based on severity of AE administer corticosteroids	
Ensure adequate evaluation to confirm etiology and/or exclude other causes
	Grade 2, 3 or 4	Permanently discontinue		
All Other irAEs	Persistent Grade 2	Withhold	
Based on severity of AE administer corticosteroids	
Ensure adequate evaluation to confirm etiology or exclude other causes
	Grade 3	Withhold or discontinue ^b		
	Recurrent Grade 3 or Grade 4	Permanently discontinue		

AE(s)=adverse event(s); CTCAE=Common Terminology Criteria for Adverse Events; DRESS=Drug Rash with Eosinophilia and Systemic Symptom; GI=gastrointestinal; IO=immuno-oncology; ir=immune-related; IV=intravenous; SJS=Stevens-Johnson Syndrome; T1DM=type 1 diabetes mellitus; TEN=Toxic Epidermal Necrolysis; ULN=upper limit of normal.

Note: Non-irAE will be managed as appropriate, following clinical practice recommendations.

^a The decision to withhold or permanently discontinue pembrolizumab monotherapy, coformulations or IO combinations is at the discretion of the investigator or treating physician. If control achieved or ≤ Grade 2, pembrolizumab monotherapy, coformulations or IO combinations may be resumed.

^b Events that require discontinuation include, but are not limited to: Guillain-Barre Syndrome, encephalitis, myelitis, DRESS, SJS, TEN and other clinically important irAEs (eg, vasculitis and sclerosing cholangitis).

Dose Modification and Toxicity Management of Infusion Reactions Related to Pembrolizumab

Pembrolizumab may cause severe or life-threatening infusion-reactions including severe hypersensitivity or anaphylaxis. Signs and symptoms usually develop during or shortly after drug infusion and generally resolve completely within 24 hours of completion of infusion. Dose modification and toxicity management guidelines on pembrolizumab associated infusion reaction are provided in [Table 5](#).

Table 5 Pembrolizumab Infusion Reaction Dose Modification and Treatment Guidelines

NCI CTCAE Grade	Treatment	Premedication at Subsequent Dosing
Grade 1 Mild reaction; infusion interruption not indicated; intervention not indicated	Increase monitoring of vital signs as medically indicated until the participant is deemed medically stable in the opinion of the investigator	None
Grade 2 Requires therapy or infusion interruption but responds promptly to symptomatic treatment (eg, antihistamines, NSAIDs, narcotics, IV fluids); prophylactic medications indicated for ≤ 24 hrs	
Stop Infusion
 
Additional appropriate medical therapy may include but is not limited to:
 
 IV fluids Antihistamines NSAIDs Acetaminophen Narcotics 
Increase monitoring of vital signs as medically indicated until the participant is deemed medically stable in the opinion of the investigator.
 
If symptoms resolve within 1 hour of stopping drug infusion, the infusion may be restarted at 50% of the original infusion rate (eg, from 100 mL/hr to 50 mL/hr). Otherwise dosing will be held until symptoms resolve and the participant should be premedicated for the next scheduled dose.
 
Participants who develop Grade 2 toxicity despite adequate premedication should be permanently discontinued from further study drug intervention.
	
Participant may be premedicated 1.5 h (± 30 minutes) prior to infusion of study intervention with:
 
Diphenhydramine 50 mg PO (or equivalent dose of antihistamine).
 
Acetaminophen 500-1000 mg PO (or equivalent dose of analgesic).

NCI CTCAE Grade	Treatment	Premedication at Subsequent Dosing
Grades 3 or 4 Grade 3: Prolonged (ie, not rapidly responsive to symptomatic medication and/or brief interruption of infusion); recurrence of symptoms following initial improvement; hospitalization indicated for other clinical sequelae (eg, renal impairment, pulmonary infiltrates) Grade 4: Life-threatening; pressor or ventilatory support indicated	Stop Infusion. Additional appropriate medical therapy may include but is not limited to: Epinephrine** IV fluids Antihistamines NSAIDs Acetaminophen Narcotics Oxygen Pressors Corticosteroids Increase monitoring of vital signs as medically indicated until the participant is deemed medically stable in the opinion of the investigator. Hospitalization may be indicated. **In cases of anaphylaxis, epinephrine should be used immediately. Participant is permanently discontinued from further study drug intervention.	No subsequent dosing
Appropriate resuscitation equipment should be available at the bedside and a physician readily available during the period of drug administration. For further information, please refer to the Common Terminology Criteria for Adverse Events v4.0 (CTCAE) at http://ctep.cancer.gov		

Other Allowed Dose Interruption for Pembrolizumab

Pembrolizumab may be interrupted for situations other than treatment-related AEs such as medical / surgical events or logistical reasons not related to study therapy. Participants should be placed back on study therapy within 3 weeks of the scheduled interruption, unless otherwise discussed with the Sponsor. The reason for interruption should be documented in the participant's study record.

6.6.2 Guidance for Management of Hepatic Events of Clinical Interest

Hepatic ECIs (HECIs) have been described in Section 8.4.7. All of these HECIs will require holding study intervention and notification of the Sponsor within 24 hours. All cases of retreatment after interruption of study intervention for HECI must be reported to the Sponsor and recorded in the database.

Immediate assessment if HECI:

All Participants

- All participants should be considered for evaluation according to the directions below within 72 hours of the alert for a non-overdose ECI. For laboratory assessments of HECIs, central laboratory is preferred; local laboratory is acceptable if central laboratory is not available.
- Procedures:
 - Consider obtaining a consultation with a hepatologist
 - Obtain a workup for hepatitis if there is no underlying hepatitis, including hepatitis A, B, C, D, E, Epstein-Barr virus, and cytomegalovirus
 - Assess for ingestion of drugs/supplements with hepatotoxic potential
 - Assess for alcohol ingestion
 - Assess for potential bacterial infection, biliary obstruction, or occult gastrointestinal bleeding
 - Repeat ALT, AST, total bilirubin, direct bilirubin, alkaline phosphatase, glutamyl transpeptidase, international normalized ratio (INR), and complete blood count with differential
 - Measure HCV RNA viral load
 - HBV DNA, HbsAg, HbeAg, anti-HBc (total and IgM), anti-Hbe, and anti-HBs regardless of prior HBV status (Note: participants should be questioned about compliance with the use of antiviral agents)
 - Other laboratories or imaging studies as clinically indicated
 - Consider liver biopsy if indicated

HCC patients are at risk for a range of complications that can cause hepatic laboratory abnormalities with or without clinical decompensation. Those with a history of chronic HCV or HBV infection also have the potential to experience virologic flares. Immune-related hepatitis has been observed in approximately 1% of participants who received pembrolizumab. The following section provides further guidance on the diagnosis and management of potential hepatic complications among HCC participants in this study.

Management of HECI for Pembrolizumab/Placebo

	Diagnosis	Management
Hepatitis B consider flare or change in HBV immunologic status	Rapid elevation of ALT to >5×ULN and/or >3× baseline	
Interrupt pembrolizumab/placebo intervention for up to 12 weeks.
 
Start antiviral therapy or check for compliance if HBV is detectable.
 
Measure safety laboratory test results for AST, ALT, ALP, T Bili, D Bili, and INR on weekly basis.
 
Measure HbsAg and HBV DNA on weekly basis (if detected at the time of onset of ECI).
 
Evaluate the following every 2-3 weeks:
 
 anti-Hbe, Hbe antigen, anti-HBs, and HBV viral load (if not detected at the onset of ECI) 
Restart pembrolizumab/placebo intervention only if ALT returns to normal or Grade 1 (if normal at baseline), or to baseline grade (if Grade 2 at baseline) within 12 weeks, and the participant is clinically stable; otherwise, the participant should be permanently discontinued.

Hepatitis C exacerbation in participants with HCV RNA positive	Rapid elevation of ALT to >5×ULN and/or >3× baseline	
Interrupt pembrolizumab/placebo intervention for up to 12 weeks.
 
Assess use of injection or inhalation drugs.
 
Recheck HCV genotype at the time of relapse of HCV viral load to rule out new infection.
 
Measure safety laboratory test results for AST, ALT, ALP, T Bili, D Bili, and INR on weekly basis
 
Measure HCV viral load every 2 weeks.
 
Please discuss risk-benefit with Sponsor prior to starting HCV antiviral therapy.
 
Restart pembrolizumab/placebo intervention only if ALT returns to normal or Grade 1 (if normal at baseline), or to baseline grade (if Grade 2 at baseline) within 12 weeks, and the participant is clinically stable; otherwise, the participant should be permanently discontinued.

Relapse of HCV infection for participants with successfully treated or new HCV infection	If HCV RNA was TND at baseline, and now has confirmed detectable HCV RNA (2 specimens, 1 week apart)	
Interrupt pembrolizumab/placebo study intervention for up to 12 weeks.
 
Start IV corticosteroid 60 mg/day of prednisone or equivalent followed by oral corticosteroid.
 
Monitor with biweekly laboratory tests, including AST, ALT, T Bili, D Bili, ALP, and INR.
 
Restart pembrolizumab/placebo intervention only if:
 
 Abnormal laboratory values resolve to Grade ≤1 or baseline (if abnormal at baseline) Taper steroid over 28 days Steroid treatment is tapered to prednisone <10 mg/day or equivalent 
Permanently Discontinue pembrolizumab/placebo intervention if:
 
 Laboratory abnormalities do not resolve within 3 weeks Steroids cannot be lowered to ≤10 mg/day (or prednisone equivalent) within 12 weeks Decompensation to CP C status
Immune-related Hepatitis	
If any of the HECI criteria is met as defined in the protocol Section 8.4.7
 
Note:
 
Immune-related hepatitis is a diagnosis made after excluding other possible etiologies such as viral flare, biliary or vascular obstruction, infection, medications, and alcohol use usually immune-related hepatitis response to dechallenge and/or steroids and re-occurs with rechallenge
	
Interrupt pembrolizumab/placebo study intervention for up to 12 weeks.
 
Start IV corticosteroid 60 mg/day of prednisone or equivalent followed by oral corticosteroid.
 
Monitor with biweekly laboratory tests, including AST, ALT, T Bili, D Bili, ALP, and INR.
 
Restart pembrolizumab/placebo intervention only if:
 
 Abnormal laboratory values resolve to Grade ≤1 or baseline (if abnormal at baseline) Taper steroid over 28 days Steroid treatment is tapered to prednisone <10 mg/day or equivalent 
Permanently Discontinue pembrolizumab/placebo intervention if:
 
 Laboratory abnormalities do not resolve within 3 weeks Steroids cannot be lowered to ≤10 mg/day (or prednisone equivalent) within 12 weeks Decompensation to CP C status

	Diagnosis	Management
Other Causes	
Rule out infection with blood, urine, and ascites culture – antibiotics should be started if infection is found
 
If total bilirubin is elevated, imaging should be obtained to rule out vascular compromise, biliary obstruction, and/or tumor progression by imaging
 
Ruled out alcohol use and hepatotoxic drugs including herbal and alternative medications
	
Restart pembrolizumab/placebo only if laboratory values have returned to Grade 1 or baseline (if normal or Grade 1 at start) or to baseline grade within 3 weeks.
 
If biliary obstruction is present, consultation with a gastroenterologist and/or an interventional radiologist should be obtained to see if the obstruction may be relieved.

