3 HYPOTHESES, OBJECTIVES, AND ENDPOINTS

In participants at least 18 years of age with hepatocellular carcinoma (HCC) and complete radiological response after surgical resection or local ablation:

Objectives	Endpoints
Primary	
Objective: To compare recurrence-free Survival (RFS). Hypothesis (H1): Pembrolizumab is superior to placebo with respect to RFS as assessed by blinded independent central review (BICR).	RFS: the time from randomization to first documentation of disease recurrence (local, regional, or distant) as assessed by BICR or by pathology consistent with HCC, or death due to any cause (both cancer and non-cancer causes of death), whichever occurs first.
Objective: To compare overall survival (OS). Hypothesis (H2): Pembrolizumab is superior to placebo with respect to OS.	OS: The time from randomization to death due to any cause.
Secondary	
Objective: To evaluate the safety and tolerability.	Adverse events (AEs). Study intervention discontinuation due to AEs.
Objective: To compare score change from baseline in global quality of life using the European Organization for Research and Treatment of Cancer Quality of Life Questionnaire (EORTC QLQ-C30) global health status/QoL scale and EORTC QLQ-HCC18.	Scores from the global health status/ quality of life (QoL) scale on the EORTC QLQ-C30 and EORTC QLQ-HCC18.
Objective: To characterize health utilities using the EuroQoL-5 Dimension Questionnaire, 5-Level (EQ-5D-5L) healthy utility scores.	EQ-5D-5L health utility score.

Objectives	Endpoints
Tertiary/Exploratory	

CCI

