16. Has adequate organ function as defined in the following table ([Table 2](#)). Specimens must be collected within 7 days prior to C1D1.

Table 2 Adequate Organ Function Laboratory Values

System	Laboratory Value
Hematological	
Absolute neutrophil count (ANC)	$\geq 1500/\mu\text{L}$
Platelets	$\geq 60,000/\mu\text{L}$
Hemoglobin	$\geq 8.0 \text{ g/dL}^a$
Renal	
Creatinine OR Measured or calculated ^b creatinine clearance (GFR can also be used in place of creatinine or CrCl)	$\leq 1.5 \times \text{ULN}$ OR $\geq 30 \text{ mL/min}$ for participant with creatinine levels $> 1.5 \times \text{institutional ULN}$
Hepatic	
Total bilirubin	$\leq 2 \text{ mg/dL}$ OR direct bilirubin $\leq \text{ULN}$ for participants with total bilirubin levels $> 2 \text{ mg/dL}$
AST (SGOT) and ALT (SGPT)	$\leq 5 \times \text{ULN}$
Albumin ^c	$> 3.0 \text{ g/dL}$
Coagulation	
International normalized ratio (INR) OR prothrombin time (PT)	$\leq 1.5 \times \text{ULN}$ unless participant is receiving anticoagulant therapy as long as PT is within therapeutic range of intended use of anticoagulants
ALT (SGPT)=alanine aminotransferase (serum glutamic pyruvic transaminase); AST (SGOT)=aspartate aminotransferase (serum glutamic oxaloacetic transaminase); GFR=glomerular filtration rate; ULN=upper limit of normal. ^a Criteria must be met without erythropoietin dependency and without packed red blood cell (pRBC) transfusion within last 2 weeks. ^b Creatinine clearance (CrCl) should be calculated per institutional standard. ^c No albumin supplement allowed within the last 14 days. Note: This table includes eligibility-defining laboratory value requirements for treatment.	

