- Drug-related total bilirubin $>10 \times \text{ULN}$
- CP score of >9 points
- Hepatic encephalopathy
- If ascites is not manageable by intervention within 3 days
- Gastrointestinal bleeding suggestive of portal hypertension (eg, esophageal or gastric varices)

Recurrence of either intrahepatic or extrahepatic disease.

Any progression or recurrence of any malignancy, or any occurrence of another malignancy that requires active treatment

Completion of 17 treatments (approximately 1 year) with pembrolizumab versus placebo.

Note: The number of treatments is calculated starting with the first dose.

For participants who are discontinued from study intervention but continue to be monitored in the study, all visits and procedures, as outlined in the SoA, should be completed.

Discontinuation from study intervention is “permanent.” Once a participant is discontinued, he/she shall not be allowed to restart study intervention.

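### The ALT restart rule for hepatitis B flare and hepatitis C exacerbation leaves out participants whose baseline ALT was Grade 1

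*Combined protocol and SAP*

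**What the plan says.** The management table in Section 6.6.2 has five rows: hepatitis B flare, hepatitis C exacerbation, HCV relapse or new infection, immune-related hepatitis, and other causes.

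- **Hepatitis B flare and hepatitis C exacerbation.** Both cells carry the same sentence. Restart is allowed "only if ALT returns to normal or Grade 1 (if normal at baseline), or to baseline grade (if Grade 2 at baseline". Clinical stability and a 12-week limit also apply. If the test is failed, "otherwise, the participant should be permanently discontinued".
- **HCV relapse and immune-related hepatitis.** The laboratory condition for restart is "Abnormal laboratory values resolve to Grade ≤1 or baseline (if abnormal at baseline". Steroid-taper conditions apply as well.
- **Other causes.** Restart is allowed on return to Grade 1 or baseline with the qualifier "if normal or Grade 1 at start", or to the baseline grade, within 3 weeks.

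Three other provisions bear on the point. In Table 2 of Section 5.1, the row "AST (SGOT) and ALT (SGPT" sets the entry limit at 5×ULN. Section 6.6.2 opens with "All of these HECIs will require holding study intervention and notification of the Sponsor within 24 hours". Section 7.1 makes discontinuation final: "Once a participant is discontinued, he/she shall not be allowed to restart study intervention".

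**The concern.** The sentence is a closed rule: *only if* two conditions, *otherwise* permanent discontinuation. The conditions are tied to a normal baseline and to a Grade 2 baseline. A participant who entered with Grade 1 ALT, flared and came back to Grade 1 meets neither, although that is full recovery to the starting point.

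The result is out of order. The middle baseline group is treated more strictly than the groups on either side of it, and no safety reason would produce that.

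What is at stake is individual dosing. A participant could lose the rest of a one-year course that cannot be resumed, and sites could apply one sentence in different ways. Such a stop might also be counted in a secondary safety endpoint listed in Section 3, "Study intervention discontinuation due to AEs".

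**Working it through.** The plan gives no figure to reproduce, so the check compares the rules row by row.

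**1. Can a Grade 1 baseline occur?** Yes. Table 2 admits ALT up to 5×ULN. Inclusion criteria 9 and 10 admit past or ongoing HCV infection and controlled hepatitis B. Section 8.4.7 defines the ALT event separately for baselines below and at or above 2×ULN. The restart sentence itself provides for the worse Grade 2 baseline.

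**2. Does return to the participant's own baseline ALT grade meet the ALT or laboratory condition for restart?**

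| Row of the 6.6.2 table | Baseline normal | Baseline Grade 1 | Baseline Grade 2 |
|---|---|---|---|
| Hepatitis B flare | yes | **no** | yes |
| Hepatitis C exacerbation | yes | **no** | yes |
| HCV relapse or new infection | yes | yes | yes |
| Immune-related hepatitis | yes | yes | yes |
| Other causes | yes | yes | yes |

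The table compares the laboratory condition only. The steroid conditions in the third and fourth rows, and each row's time limit, apply in addition. A Grade 1 baseline is covered in 3 of 5 rows as written.

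**3. Does the grammar rescue it?** There are two readings of the first condition.

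- The parenthesis governs both *normal* and *Grade 1*. A Grade 1-baseline participant then has no route to restart, even after full normalisation.
- The parenthesis governs only *Grade 1*, and return to normal is unconditional. A Grade 1-baseline participant may then restart after full normalisation, but still not on return to Grade 1.

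Under both readings, recovery to a Grade 1 baseline leads to permanent discontinuation.

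**4. Does other text supply the missing case?** None that is visible. The resume rule in Table 4 (Section 6.6.1) is confined to non-hepatic immune-related events. The hepatitis B entry criteria and Table 16 are redacted and could not be checked. They concern hepatitis B eligibility and treatment definitions, so they would not be expected to supply an ALT restart rule for the hepatitis C row.

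**5. Cost to one affected participant.** The course is 17 doses. A stop after dose *k* forfeits 17 − *k*: at most 17 − 1 = 16, at least 17 − 16 = 1. This assumes that every remaining dose would otherwise have been given, so it is an upper bound for each *k*.

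**The case against.** The strongest reply is that few clinicians would apply the sentence literally. If Grade 1 is acceptable for someone who started normal, and Grade 2 for someone who started at Grade 2, then Grade 1 is acceptable for someone who started at Grade 1. The section is headed as guidance and the clause says *should*. Section 7.1 lists the hepatic events that force discontinuation, and failing an ALT restart threshold is not among them. Its bullet on adverse events points to Section 6.6.1, and discontinuation after a prolonged interruption is subject to agreement with the Sponsor. Hepatic events reach the Sponsor within 24 hours and every retreatment is reported. The other rows also govern different diagnoses with different conditions, so a difference between rows is not in itself a contradiction.

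Much of this stands as mitigation. Automatic loss of treatment is unlikely, and the comparison between rows shows a probable omission, not a formal conflict. It does not remove the defect. The Section 7.1 list does not override an explicit instruction in Section 6.6.2 to discontinue permanently, and notifying the Sponsor does not change what the rule says. That the intended meaning is easy to guess is a reason to write it down.

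**Conclusion.** The concern holds, as a minor point. In two of the five rows the restart rule gives the wrong answer for a participant who recovers to a Grade 1 baseline, under either reading of the sentence.

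The affected group is limited to participants with hepatitis B, or with detectable HCV RNA, who had Grade 1 ALT at baseline and then flare. The documents give no figure from which to count them. Discontinued participants remain in follow-up under Section 7.1, so the trial's efficacy conclusions are not at risk, and any effect on the count of discontinuations due to adverse events would be a few participants at most.

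The conclusion rests on the visible text and on the sentence being applied as written. It does not depend on the CTCAE cut-offs for ALT grades, which the documents do not state.

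**What to change.** In the hepatitis B flare and hepatitis C exacerbation cells, widen the first parenthesis from a normal baseline to a *normal or Grade 1* baseline. Return to normal or Grade 1 then permits restart for both groups. The Grade 2 branch, the 12-week limit, the clinical-stability condition and the discontinuation clause stay as they are. A Grade 1 baseline would then be covered in 5 of 5 rows, and the ambiguity about full normalisation disappears too.

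The cost is three added words in each of two cells at the next amendment, with no new procedure, visit or analysis. If no participant is still on treatment by then, the correction matters only where this wording is reused in later protocols.
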